5.2 Research Procedures

5.2.1 Outcomes.

Cognition: This study will involve several neuropsychological tests of cognitive functioning. Based on our pilot work, the primary neuropsychological outcome for measuring cognitive processing speed (CPS) in the current proposal will be the oral version of the Symbol Digit Modalities Test (SDMT) [35]. This test is considered a more pure measure of CPS, as it relies less on working memory (i.e., the central executive) than other neuropsychological measures that are commonly used in MS research (i.e., the Paced Auditory Serial Addition Test; PASAT) [36]. The SDMT further is a better predictor of whole-brain atrophy and T2-lesion volume than the PASAT [36]. Indeed, the SDMT has emerged as the best predictor of future cognitive decline in persons with relapsing-remitting MS [37]. As such, it is often considered to be a proxy of generalized cognitive

impairment in this population [38]. The current proposal further will include other exploratory neuropsychological measures of CPS. Those measures include the PASAT [39], modified flanker task [40], Pattern Comparison Test [41], and DKEFS Trail-Making and Color-Word Interference Tests [42]. Such measures will be included to examine the generalizability of the effects of treadmill walking exercise training on the overall construct of CPS. Those tests have strong psychometric properties (e.g., [43]), and are commonly-used to document the efficacy of cognitive rehabilitation interventions in persons with MS (e.g., [44]).

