The primary analysis will involve a statistically efficient, hierarchical step-down testing approach using ANCOVA models to examine differences in post-test outcomes of CPS and thalamocortical RSFC (i.e., examining group differences in follow-up outcomes, adjusting for baseline as covariate). The hierarchical step-down approach presents a series of conditional hypothesis tests after the primary hypothesis is assessed. This *a priori* specifies the importance and order of the testing so that each hypothesis is tested in order, until the first non-significant result occurs. Once a null-hypothesis is not rejected, all formal testing will stop, and all subsequent results will be reported as *post-hoc* and/or descriptive. This protects against Type I error as it assumes that the outcomes are correlated, and the overall *p*-value is protected by reporting the largest *p*-value for all the tests. As the primary study outcome involves CPS based on SDMT scores, we will first perform an ANCOVA model on follow-up SDMT score, with group (intervention or control) as a between-subjects factor and baseline SDMT score as the covariate. If statistically significant (i.e., *p*<.05), we will then assess the effects of the intervention on the general construct of CPS using MANCOVA and on the individual CPS tests using separate, univariate ANCOVA models.

Regarding thalamocortical RSFC, the next set of analyses will involve performing ANCOVA models on follow-up RSFC between the thalamus and frontal cortical areas (e.g., SFG, MFG [21]), respectively, with group (intervention or control) as a between-subjects factor and baseline RSFC between the thalamus and frontal cortical areas, as the covariates. We will require an alpha of .05 (corrected for multiple comparisons) for significance for thalamocortical RSFC outcomes. The correction for multiple comparisons will be achieved by establishing a suitable voxel cluster-level threshold through Monte Carlo simulations (using the 3dClustSim program, part of the AFNI suite of image analysis programs). Based on our pilot work [19,21], we expect significant group differences in SDMT score and RSFC between the thalamus and frontal cortical areas, respectively, at follow-up after controlling for baseline scores, whereby participants who are randomly assigned to the intervention group will demonstrate greater SDMT scores and stronger thalamocortical RSFC at follow-up compared with those who are randomly assigned to the control group.

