Specific Aim 1. The primary analysis will involve a statistically efficient step-down testing approach using ANCOVA models to examine changes in CPS and thalamocortical RSFC (i.e., examining group differences in follow-up outcomes, adjusting for baseline). As the primary study outcome involves CPS based on SDMT scores, we will first perform an ANCOVA model on follow-up SDMT score, with group (exercise or control) as a between-subjects factor and baseline SDMT score as the covariate. If statistically significant (i.e., $p<.05$), we will then assess the effects of the intervention on thalamocortical RSFC. This second step will involve performing two separate ANCOVA models on follow-up RSFC between the thalamus and right MFG and ACC, respectively, with group (exercise or control) as a between-subjects factor and baseline RSFC between the thalamus and right MFG and ACC, respectively, as the covariates. We will require an alpha of .05 (corrected for multiple comparisons) for significance for thalamocortical RSFC outcomes. The correction for multiple comparisons will be achieved by establishing a suitable voxel cluster-level threshold through Monte Carlo simulations (using the 3dClustSim program, part of the AFNI suite of image analysis programs). Based on our pilot work¹², we expect significant group differences in SDMT score and RSFC between the thalamus and right MFG and ACC, respectively, at follow-up after controlling for baseline scores, whereby participants who are randomly assigned to the exercise group will demonstrate greater SDMT scores and stronger thalamocortical RSFC at follow-up compared with those who are randomly assigned to the control group.

Specific Aim 2. We will examine RSFC between thalamus/right MFG, and RSFC between thalamus/ACC, respectively, as two potential mediators of the effects of TMWX training on CPS, consistent with the methodologies of Baron and Kenny⁸⁹ and MacKinnon et al⁹⁰. This statistical mediation approach is consistent with the proposed gold standard approach for examining exercise-related mechanisms of cognitive

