Exploratory Aim 3. Considering that MS-related CPS impairment substantially limits daily functioning, we now include exploratory functional outcomes in this proposal, as suggested by reviewers. As there are multiple, interrelated outcomes within this Exploratory Aim, we will perform a multivariate analysis of covariance (MANCOVA) on follow-up scores for the functional outcomes controlling for baseline values as an approach for examining the consistency of the potential intervention effects (i.e., exercise vs. control as the between-subjects factor) on this overall construct (i.e., how functional consequences of CPS impairment may change together with TMWX training). We further will explore the effects of the intervention on the individual outcomes using separate exploratory, descriptive, univariate ANCOVA models on follow-up CIQ scores (i.e., community participation), TIADL scores (i.e., ability to perform activities of daily living), MSIS-29 scores (i.e., QOL), T25FW and LSPA performance (i.e., functional mobility), respectively, with group (exercise or control) as a between-subjects factor and baseline CIQ, TIADL, MSIS-29, T25FW, and LSPA scores, respectively, as the covariates. We expect significant and consistent group differences in those functional outcomes at follow-up after controlling for baseline scores, whereby participants who are randomly assigned to the exercise group will demonstrate better follow-up scores on functional outcomes compared with those who are randomly assigned to the control group.

As MS-related cognitive impairment involves reduced performance in other cognitive domains beyond CPS, we now include exploratory cognitive outcomes beyond the SDMT in the current proposal, as suggested by reviewers. We will adopt a similar approach (see *Exploratory Aim 3 above*) to examine the effects of the intervention on the general construct of cognitive performance using MANCOVA and on the individual cognitive tests using separate univariate ANCOVA models. Effect sizes will be expressed as partial eta-squared (η_p^2) and Cohen's d ⁹². The effect sizes from the interaction terms from the ANCOVAs and correlations will serve as effect sizes for the subsequent power analyses required for informing the development of a home-based rehabilitation program using this intervention approach.

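### The protocol and the SAP set different confirmatory plans for thalamocortical RSFC, a primary outcome, and neither says which governs

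*Combined protocol and SAP*

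**What the plan says.** The protocol's Abstract and the SAP's opening section (Statistical Design and Power) both name SDMT and thalamocortical RSFC as the primary outcomes. The two texts then differ.

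- **Regions, protocol 5.3 Analysis.** The models are for "follow-up RSFC between the thalamus and frontal cortical areas (e.g., SFG, MFG [21"; the bracketed areas are examples and no side is given. Protocol 5.2.1 says only thalamus and frontal cortex.
- **Regions, SAP Specific Aim 1.** There are to be "two separate ANCOVA models on follow-up RSFC between the thalamus and right MFG and ACC, respectively". Specific Aim 2 uses the same two connections as mediators.
- **Order, protocol 5.3.** After a significant SDMT, "we will then assess the effects of the intervention on the general construct of CPS using MANCOVA", then the individual CPS tests. In a new paragraph on RSFC, "the next set of analyses will involve performing ANCOVA models on follow-up RSFC". The general rule is: "Once a null-hypothesis is not rejected, all formal testing will stop". Later results then become post hoc or descriptive.
- **Order, SAP Specific Aim 1.** After a significant SDMT, "we will then assess the effects of the intervention on thalamocortical RSFC".
- **Status of the other cognitive tests.** Protocol 5.2.1 says the study "further will include other exploratory neuropsychological measures of CPS". The SAP, under Exploratory Aim 3, says "we now include exploratory cognitive outcomes beyond the SDMT in the current proposal".
- **Correction.** Both texts require .05 corrected for multiple comparisons for the RSFC outcomes, through a 3dClustSim cluster-level threshold. Neither states the mask. Protocol 5.3 adds that the overall p-value is protected because the largest p-value among the tests is reported. The SAP does not repeat this.

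**The concern.** A primary outcome needs one definition and one place in the testing order, fixed before the data are seen by group. Here there are two of each. MFG is in both texts, SFG only in the protocol, and ACC and the right side only in the SAP. A reader cannot tell which thalamic connections are confirmatory.

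The order matters because the protocol attaches a stop rule to it and does not exempt the CPS tests. If that rule is taken literally, the same data could make an RSFC result confirmatory under the SAP and post hoc under the protocol, and the tests standing in the way would be ones that the protocol itself calls exploratory.

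A smaller gap lies across the regions. A cluster threshold controls error over the voxels of one searched map. With two separate models and no stated mask, the texts do not show that it covers both regions, or whether one significant region is enough for a claim.

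**Working it through.** **1. The plan's own figure.** Inputs from SAP, Sample Size Considerations: partial eta-squared 0.11, alpha .05, power 0.80, two groups, one covariate, 75% retention. f² = 0.11/0.89 = 0.1236. Noncentral F with λ = N × f² and df = (1, N − 3). At N = 66, λ = 8.16 and power is 0.803; 66 is the smallest N that reaches 0.80. Then 66/0.75 = 88. Both stated figures reproduce, and nothing below changes them.

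**2. The two plans side by side.**

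| | Protocol 5.3 | SAP Aim 1 |
|---|---|---|
| Regions | SFG, MFG as examples | MFG and ACC, exactly |
| Side | none | right (for MFG) |
| Step after SDMT | CPS MANCOVA, individual CPS tests | RSFC |
| General stop rule | yes, no exemption | not repeated |
| Explicit condition | SDMT p<.05 | SDMT p<.05 |

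No section says which text prevails. They also differ elsewhere: 65 against 72 participants at the second site, and the Lawton-Brody IADL against the TIADL. So it cannot be assumed that one was conformed to the other.

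**3. How much the order could matter (illustration).** Assumptions: the stop rule is read literally, SDMT is significant (its power set at 0.803), all tests are equally correlated, and the five other CPS tests named in protocol 5.2.1 must all be significant. These are the PASAT, flanker, Pattern Comparison, Trail-Making and Color-Word tests. The MANCOVA step is not counted. With independence and 80% power each, 0.80^5 = 0.33. The correlated cases come from 2,000,000 simulated draws.

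| Power per CPS test | Correlation 0 | 0.5 | 0.7 |
|---|---|---|---|
| 80% | 33% | 60% | 71% |
| 50% | 3% | 20% | 30% |

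The entries are the chance that RSFC is still formally testable. Under the SAP it is 100%. The documents give neither power nor correlation for these tests, and the result depends heavily on both.

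**4. How much the rule across regions could matter (illustration).** Assumptions: two regions, no true RSFC effect, SDMT already passed, and each region judged at an uncorrected two-sided .05, which neither text says. With independence, at least one false claim has probability 1 − 0.95² = 9.75%, in the hypothesised direction 1 − 0.975² = 4.9%, and both regions 0.05² = 0.25%. Correlated values are from a bivariate normal.

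| Correlation | At least one | At least one, hypothesised direction | Both |
|---|---|---|---|
| 0 | 9.75% | 4.9% | 0.25% |
| 0.7 | 8.3% | 4.2% | 1.7% |
| 0.9 | 7.0% | 3.5% | 3.0% |

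For one test the references are 5% and, in one direction, 2.5%. Requiring both regions, or testing them in a fixed order, gives no inflation. If SDMT has no true effect, familywise error stays at or below 5%, because RSFC is reached only through a significant SDMT.

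**The case against.** The strongest reply is that the texts can be read together.

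- **Regions.** The protocol's areas are examples, so the SAP may simply narrow them, and the SAP is closed and consistent with its own Aim 2. A reader might infer that the lists exclude each other. They do not: MFG is common, and an open list does not rule out ACC. What stands is that the protocol's list does not prespecify a primary outcome and no text says that the SAP's list replaces it.
- **Order.** The only explicit condition in protocol 5.3 is on SDMT, RSFC opens its own paragraph, and the other CPS tests are exploratory. A reader might infer that the protocol definitely makes those tests gates to RSFC. It does not say so. The point follows only from its stop rule, its sequence and the missing exemption. That is enough to need one clarifying sentence.
- **Multiplicity.** A reader might infer that RSFC has no correction, or that its false-positive rate is 9.75%. Neither is supported, since both texts require a corrected .05. The protocol's sentence on the largest p-value may even mean that every region must be significant, which gives no inflation. But it gives no order of regions and is not applied to them explicitly, and the SAP does not carry it. So the gap across regions stands with moderate confidence only.

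**Conclusion.** The protocol and the SAP differ on the regions for a primary outcome and on what is tested before it, and nothing says which governs. That much rests on the text alone. The consequence of the order, that RSFC could be post hoc under one text and confirmatory under the other, holds only if the protocol's stop rule is applied literally to the exploratory CPS tests. The missing mask and the unclear rule across regions are a lesser gap, held with moderate confidence.

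The percentages for CPS blocking and for false regional claims show how far the choices could matter under assumed power, correlation and uncorrected testing. They are not estimates for this trial. The SDMT conclusion, the 66 and the 88 are untouched. This should be settled before analysis, but it does not threaten the trial's first primary test.

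**What to change.** Before any analysis by group, amend protocol 5.3 and SAP Specific Aims 1 and 2 so that they:

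1. State which text governs.
2. Carry one closed region list, with side, matching the Aim 2 mediators. The SAP's list already does this.
3. Give one order: RSFC directly after SDMT, with the exploratory CPS tests outside the formal chain, in line with their stated status.
4. Name one rule across the two regions: a fixed order, both required, Holm at .05, or, if testing is voxelwise, one 3dClustSim threshold over a single stated mask that covers both.

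No new data are needed. The cost lies in what can be claimed:

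- **Fixed order:** the second region cannot be claimed if the first fails.
- **Both required:** at partial eta-squared 0.11 and independent regions, power is 0.803² = 0.64 with 66 completers; positive correlation raises it.
- **Holm:** worst-case power per region (tested at .025) at the same effect falls from 0.80 to 0.71 with 66 completers. At the intent-to-treat N of 88 (λ = 88 × 0.1236 = 10.88) it falls from 0.90 to 0.84, before any dilution from carrying values forward.

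The SAP says the pilot RSFC effects were larger than 0.11, so these power figures lean to the cautious side.

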5.1.1. Sample Size. We plan to enroll 88 fully-ambulatory persons with MS (i.e., 44 per condition) who have objective impairment in CPS; this is based on a power analysis and presumed 25% attrition. Of the 88 total participants, 65 will be recruited at Kessler Foundation, as this study is currently ongoing and was partially completed at the University of Alabama at Birmingham. The minimal sample size of 66 persons with MS (i.e., 33 per condition) was determined based on power analysis using previous effect sizes from our preliminary RCT of TMWX training on CPS outcomes (i.e., $\eta_p^2=0.11$) and standard assumptions of Type I error (0.05) and power (0.80) based on analysis of covariance (ANCOVA) on follow-up SDMT scores, controlling for baseline SDMT score [19]. We note that this rate of attrition exceeds that of the overall average of exercise training studies among persons with MS based on a systematic review [28] making our calculations conservative.

5.1.2. Recruitment. Prospective participants will be recruited directly through the community, local chapter of the National MS Society (NMSS), and our laboratory database of previous participants with MS who have inquired about participating in future studies. Advertisements for the study will be distributed through local MS centers, facilitators of local MS support groups, *MS Connection* publications, and e-mail distributions. As a backup plan, we may recruit prospective participants with MS through the North American Research Committee on Multiple Sclerosis (NARCOMS) patient registry or iConquerMS if enrollment is slow.

5.1.3. Screening. The screening process for potential participants will first involve a phone screen, followed by an in-person screen. Via telephone, the project coordinator will obtain the following information from potential participants:

- Age between 18-59 years
- Definite diagnosis of MS
- Relapse-free for 30 days, not acutely taking corticosteroids
- No major depressive disorder, schizophrenia, bipolar disorder I or II, substance abuse disorder
- Not currently taking medications that can affect cognition (i.e., benzodiazepines, anti-psychotics)
- Not having known/diagnosed cardiovascular, metabolic, or kidney disease
 - If the prospective participant does report having known/diagnosed cardiovascular, metabolic or kidney disease, then physician's approval will be required in order to be eligible for study enrollment.

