- Confirmation of on at least 6-months of a stable disease-modifying therapy (DMT) regimen
- Right-handedness
- Not engaging in at least 150 minutes of moderate-to-vigorous physical activity behavior
- Not currently engaging in cognitive rehabilitation or participating in regular brain fitness activities
- Not currently pregnant

If a participant passes the above inclusion/exclusion criteria, the project coordinator will then administer the TICS-M over the phone to ensure that all participants are not decisionally impaired. In order to pass this inclusion criterion, participants must demonstrate TICS-M scores of 18 or higher. We further will administer the Mini Mental State Examination (MMSE) during the in-person screen to confirm a lack of decisional-impairment (see 5.2 Research Procedures below). If participants are not decisionally impaired, the project coordinator will request contact information for the potential participant's neurologist, whereby they will email or fax a letter asking them to verify a definite MS diagnosis and confirmation that the participant has been on a stable DMT regimen for at least 6-months. Upon receipt of these materials from the participant's neurologist, we will perform an in-person screening visit after informed consent is provided (See 5.2 Research Procedures below). If a participant does not qualify for the study, they will be notified via telephone and asked if they would be willing to be contacted for future research opportunities from our laboratory.

5.1.4 Randomization. As this study represents a RCT, participants will be randomly assigned to either a treadmill walking exercise or active control condition. We anticipate that 44 participants will be randomly assigned to each condition. Briefly, the treadmill walking exercise condition will involve supervised treadmill walking exercise that progresses in terms of duration and intensity over the course of 3-months. Participants will attend 36 sessions that will each last approximately 60 minutes, and will take place 3-times per week. The active control condition will involve supervised stretching-and-toning activities that will occur over the course of 3-months. Participants will attend 36 sessions that will each last approximately 60 minutes, and will take place 3-times per week.

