5.2.2 Protocol Overview. The proposed study involves a single-blind, randomized controlled trial (RCT) design. Participants will undertake baseline assessments, and will then be randomly assigned into either the 3-month intervention or 3-month active control condition. Following the 3-month study period, participants will return to the laboratory and complete follow-up outcome measures (i.e., the same measures as baseline, using alternate forms where applicable) by assessors who are unaware of which condition participants were randomly assigned to.

5.2.3 Baseline Testing. The baseline outcome assessments will be spread out across 2 visits for minimizing fatigue and interference from cognitive tests. There will be approximately 2 days separating each of these testing visits. Collectively, baseline testing will involve completion of the in-person screening measures, neuropsychological tests, measures of walking, physical function tests, questionnaires, cardiorespiratory fitness test, and MRI scan. Importantly, all data collection will be done in-person, and will not involve collection of data from medical records.

5.2.3.1 Baseline Visit 1: In-Person Screening Session. Once the project coordinator receives the verification of the participant's definite MS diagnosis and confirmation of being on at least 6-months of a stable DMT regimen, the project coordinator will schedule the participant for the first baseline testing visit via telephone—this will also include several in-person screening measures that will take place at the outset of this session. Baseline Visit 1 (i.e., including the in-person screening component) will occur at Kessler Foundation. Participants will complete the following procedures during the in-person screening session within the first baseline testing visit:

- Participants will first provide written informed consent
- Participants will then undertake the MMSE
 - In order to participate in the remainder of the study, participants will demonstrate scores of 21 or higher
- Participants will then undertake the SDMT
 - The SDMT involves pairing 9 abstract geometric symbols with single-digit numbers as quickly and accurately as possible over 90 seconds
 - In order to participate in the remainder of the study, participants will demonstrate slowed CPS based on SDMT scores at least 1 SD below the regression-based normative score for healthy controls (i.e., 16th percentile)

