Sample Size Considerations. As described in the original application (i.e., R01HD091155-A1), we conducted a conventional power analysis using G*Power (Version 3.1.9.5) and estimated the appropriate sample size for detecting differences in follow-up SDMT scores, controlling for baseline score (Specific Aim 1). Using G*Power, this was accomplished using the 'F test' selection within the 'Test' family menu, and the Statistical Test of 'ANCOVA: Fixed effects, main effects and interactions'. The effect size ($\eta_p^2=0.11$) for the power analysis was computed from our pilot RCT¹² of TMWX training compared with a waitlist control condition on SDMT scores in persons with MS who had mild ambulatory disability, but not CPS impairment. That effect size was smaller than the effect sizes for thalamocortical RSFC outcomes, and thus was included in the main power analysis as a conservative approach. The power analysis included standard assumptions of alpha (0.05) and beta (0.80). The power analysis indicated that the minimal total sample size for testing group differences on follow-up SDMT scores, controlling for baseline scores should be 66 participants (33 per group). This supports our goal of recruiting 88 participants (44 per condition) as yielding adequate power, based on retention of 75% of the enrolled participants. The current application proposes a change of grantee organization whereby the final 72 participants will be enrolled at KF. We will explore the possible influence of study site on the outcomes in *post-hoc* sensitivity analyses. We expect that the effects of study site are likely negligible given the constants of the study team and standardized manuals of operating procedures that guide all study aspects.

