improvement at the brain-systems level in the general population²⁸. As pre-conditions of the mediation analysis, we will first perform correlations among group (i.e., exercise or control), change in SDMT scores, and change in RSFC between the thalamus and right MFG and ACC, respectively, using Spearman's rho rank-order correlations (ρ)⁹¹ to test if those outcomes are interrelated. Consistent with our pilot work¹², we expect that TMWX training will be associated with improvements in CPS and increases in thalamocortical RSFC. Moreover, we expect that improvements in CPS will be associated with increases in thalamocortical RSFC. Then, to establish mediation, we will perform hierarchical linear regression models for evaluating each of the two mediators (i.e., changes in RSFC between thalamus/right MFG, and RSFC between thalamus/ACC, respectively), separately. This will involve regressing change in SDMT score on group in Step 1 and then adding change in the mediator in Step 2. In order to establish mediation, if the pre-conditions are met, group must influence change in SDMT in Step 1, and the mediator must influence change in SDMT score in Step 2 of the regression as well as attenuate the effect of group on SDMT scores (i.e., the effect of group on SDMT should be reduced and become non-significant between Step 1 and Step 2)⁸⁹. As such, we expect significant effects of group on change in CPS, and that the effect of group (i.e., exercise or control) on change in CPS will be attenuated, but not reach zero, when accounting for the effects of changes in thalamocortical RSFC. In other words, we expect that changes in thalamocortical RSFC will be partial mediators of the effects of TMWX training on CPS in persons with MS with impaired CPS.

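### Aim 2 tests mediation on change scores with no baseline term, so its pass/fail conditions can disagree with the baseline-adjusted Aim 1 ANCOVA of the same group effects

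*Combined protocol and SAP*

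**What the plan says.** The SAP under Specific Aim 1 fits an ANCOVA to follow-up SDMT "with group (exercise or control) as a between-subjects factor and baseline SDMT score as the covariate". It treats follow-up RSFC the same way, with baseline RSFC as covariate. Protocol section 5.3 has the same form.

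The SAP under Specific Aim 2 changes form. It first requires Spearman correlations among group, change in SDMT and change in RSFC. It then sets out the regression: "This will involve regressing change in SDMT score on group in Step 1 and then adding change in the mediator in Step 2". Mediation is claimed only if these pre-conditions are met, group affects SDMT change in Step 1, and the mediator affects it and weakens the group effect in Step 2.

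The SAP's Statistical Analysis paragraph lists covariates to be added if the groups differ on them: disease duration, BMI, age, sex, cognitive reserve, lesion volume and relapse rate. Baseline SDMT and baseline RSFC are not on the list.

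On entry, protocol section 5.2.3.1 requires that "participants will demonstrate slowed CPS based on SDMT scores at least 1 SD below the regression-based normative score for healthy controls". The later Visit 1 and Visit 2 test lists do not repeat the SDMT, so the screening score is also the baseline score.

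**The concern.** Aims 1 and 2 ask the same two questions (did exercise move SDMT, did it move RSFC) with different tests. A change score in effect fixes the baseline slope at 1; ANCOVA estimates it. Unless the true slope is 1, the change score carries extra noise tied to baseline, and the test has less power.

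Aim 2 uses these tests as pass/fail conditions. The trial could therefore report under Aim 1 that exercise raised RSFC, and then halt the mediation analysis under Aim 2 because the same effect was not significant. Specific Aim 2 has no rule for that case.

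A second issue concerns the mediator–outcome slope in Step 2. Randomisation does not protect this slope. Change in SDMT and change in RSFC each contain their own baseline, so if the two baselines are correlated, the two changes can be associated even when RSFC has no effect on SDMT.

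**Working it through.** **Inputs from the documents.** Alpha 0.05, power 0.80, partial eta-squared 0.11 for baseline-adjusted SDMT, minimum N of 66 (33 per group). The effect comes from a pilot in people "who had mild ambulatory disability, but not CPS impairment". The SAP says it was smaller than the pilot effects for RSFC, but gives no RSFC value.

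**Assumed inputs.** The baseline/follow-up correlation r and the correlation between baseline SDMT and baseline RSFC are not in the documents, so ranges are used.

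**1. The plan's figure.** f² = 0.11/0.89 = 0.1236. With noncentrality f² × N, 1 numerator and N − 3 denominator degrees of freedom, power is 0.797 at N = 65 and 0.803 at N = 66. The plan's 66 is reproduced, and 66/0.75 = 88.

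**2. RSFC (nobody is selected on it).** With equal variances, the residual variance of change relative to ANCOVA is 2(1 − r)/(1 − r²) = 2/(1 + r), which is 1.54, 1.33 and 1.18 at r = 0.3, 0.5 and 0.7. Divide f² by this ratio and use N − 2 = 64 degrees of freedom:

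| Partial eta-squared | ANCOVA power | Change, r = 0.3 | r = 0.5 | r = 0.7 |
|---|---|---|---|---|
| 0.11 | 80% | 62% | 68% | 74% |
| 0.15 | 92% | 77% | 83% | 87% |
| 0.20 | 98% | 90% | 93% | 96% |

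In simulated trials at 0.11, ANCOVA was significant and change was not in about 20%, 14% and 8% of trials (r = 0.3, 0.5, 0.7); the reverse occurred in about 2.5%. At 0.20 the ANCOVA-only figures fall to 8%, 5% and 2%. All of this ignores the cluster-level correction that Specific Aim 1 applies to RSFC.

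**3. SDMT (selected at entry).** Selection narrows the baseline variance to a fraction v, and the ratio becomes [(1 − r)²v + 1 − r²]/(1 − r²). Example: a cut at the MS population mean gives v = 0.363; at r = 0.7 the ratio is (0.09 × 0.363 + 0.51)/0.51 = 1.06, against 1.18 without selection.
- With reliability 0.75–0.90 and an MS mean 0.75–1 SD below the healthy norm (assumed), the variance penalty is 2–5%. Power is then 0.795–0.784 against 0.803, a loss of about 1–2 points.
- Over r = 0.5–0.9 and cuts from −1 to +1 SD of the MS mean, power is 0.80–0.73. The loss passes 5 points only at the lowest r with the mildest cut.
- Simulated disagreement with the cut at 0 or −1 SD runs both ways: ANCOVA only in 1.5–6.6% of trials, change only in 1.6–2.3%.
- Passing both Step 1 and the Spearman group-by-change condition has probability 0.72–0.76 with those cuts.

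**4. Type I error for the group effect.** With no true effect, ANCOVA and Step 1 each reject in about 5% of simulated trials, with or without selection.

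**5. Mediator–outcome slope.** RSFC was given no effect on SDMT, the baselines were correlated at 0.2–0.4, r was 0.6–0.8 for SDMT and 0.4–0.5 for RSFC. The change-score model then declares a slope in 5.9–11.2% of trials without selection, or about 5–13% allowing for simulation error. With selection it is about 5–6%. With both baselines in the model it is about 5%.

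**6. Effect of adding baseline.** Regressing follow-up minus baseline on group and baseline only lowers the baseline coefficient by 1. The group coefficient and p-value are those of the Aim 1 ANCOVA, which a numerical check confirmed. Step 1 power returns to 0.803.

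**The case against.** Several points on the other side are sound.

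- **Selection.** A reader might infer that admitting people on a low SDMT, then using that score as baseline, biases Aim 2 through regression to the mean. It does not bias the group comparison. The expected rise (0.10–0.24 normative SD under the assumptions in step 3) occurs in both randomised arms, and selection makes the SDMT penalty smaller. That argument applies only to uncontrolled change within an arm.
- **Baseline imbalance.** A reader might also infer that chance imbalance biases change scores but not ANCOVA. Over repeated randomisation both are unbiased; they differ only conditional on the imbalance observed.
- **Size for RSFC.** The 62–74% row uses the SDMT effect, which the SAP says is smaller than the RSFC effects. It is the pessimistic end. The planned RSFC test also carries a cluster-level correction, so the disagreement rates are only indicative.
- **Meaning of change.** Specific Aim 1 glosses changes as follow-up differences adjusted for baseline, and Specific Aim 2 does not define the term. Raw change is therefore an inference. It is the natural one: a Spearman correlation and a mediator term need a value for each person, which a group contrast from ANCOVA does not supply, and no residualised score is described.
- **Reach.** The efficacy conclusion rests on Aim 1. Aim 2 concerns mechanism.

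These points limit the size of the concern. They do not supply the missing baseline terms or a rule for disagreement.

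**Conclusion.** The point holds as a modest one about efficiency and consistency, with a secondary confounding issue in Step 2. As written, Aim 2 can stop for lack of a group effect that Aim 1 has found or, less often, the reverse. For SDMT the cost is small: about 1–2 power points under the assumed selection, and usually under 5. For RSFC it ranges from 6–18 points if the effect is no larger than 0.11 to 2–8 points at 0.20, assuming r = 0.3–0.7, n = 66 and no cluster correction. The RSFC effect and r are not given, so no single figure can be defended. The mediator–outcome false-positive rate rests on the assumed correlation between baselines, and is close to nominal once selection on SDMT is allowed for.

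The documents do not support a claim of inflated type I error for the randomised effect, or of any damage to the Aim 1 result. The change is still worth making, because Aim 2 carries its own hypothesis and the remedy is nearly free.

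**What to change.** Restate Specific Aim 2 with these models:

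- **Step 1 (total effect):** follow-up SDMT on group + baseline SDMT, identical to the Aim 1 ANCOVA.
- **Mediator model, for each RSFC pair:** follow-up RSFC on group + baseline RSFC, as in the Aim 1 RSFC ANCOVA. Baseline SDMT should stay out of this model, or the two RSFC tests could still differ.
- **Step 2:** follow-up SDMT on group + follow-up RSFC + baseline SDMT + baseline RSFC.

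Drop the unadjusted Spearman group-by-change pre-conditions and take the group effects from these models; otherwise the Spearman tests could still contradict Aim 1. If change scores are kept for description, define them.

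The cost is SAP wording, plus one degree of freedom in Step 1 and in the mediator model and two in Step 2. Every variable is already collected.
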